Planned Sample Size:	A sample size of 112 subjects per group is calculated to achieve a power of more than 80% for proof of equivalence for both co-primary endpoints. Considering 2 stratification factors i.e. body weight (Kg): ≤58, 59-74 & ≥75, Hb level (g/dl): 10 – 11 & > 11 – 12 and to balance between the two treatment groups in Thailand and Russia, the total number of subjects to be randomized is estimated to be 264 (n=132 subjects in each group) since a drop-out rate of approximately 18% was expected. The subjects will be randomized into two groups (n=132 subjects in each group) in a 1:1 ratio.
Dosage Form, Dose and Route of Administration of IP:	EPIAO injection will be administrated intravenously one to three times a week at the end of dialysis session for a period of 52 weeks. The maximum allowable dose is 300 IU/kg/week.
Dosage Form, Dose and Route of Administration of comparator:	EPIAO injection will be administrated intravenously one to three times a week at the end of dialysis session for a period of 52 weeks. The maximum allowable dose is 300 IU/kg/week.
Study Endpoints:	
Primary endpoint
 
Mean absolute change in haemoglobin level from baseline to 6 months after treatment with EPIAO/EPREX in parallel groups (g/dl).Mean absolute change in weekly epoetin dosage per kg body weight from baseline to 6 months after treatment with EPIAO/EPREX in parallel groups (IU/kg/week) 
Secondary Endpoints:
 
Proportion of subjects hemoglobin values are within 10 - 12 g/dl for the last 4 weeks of the period for assessment of treatment of efficacy and safety (weeks 32-36)

	
• Proportion of subjects with any haemoglobin measurement outside the target range during the double-blind treatment period• Mean hemoglobin and hematocrit levels every 4 weeks within treatment period (52 weeks)• Mean doses of the study products (IU/kg/week) every 4 weeks throughout the study period (52 weeks)• Incidence of blood transfusions 
Safety endpoints:
 
• Incidence and nature of adverse events• Incidence of drug related adverse events• Clinically significant changes in the vital signs, physical and laboratory examination• Number of subjects who prematurely withdrew from the study due to AE and SAE• Number of subjects with presence of anti-erythropoietin antibodies (anti-EPO Ab)

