4.1.1 Inclusion Criteria at Screening

Subjects must satisfy all of the following criteria to be included in the study:

1. Male and female subjects between the age of 18 to 75 years
2. Subjects with end stage renal disease (CKD stage 5*) on epoetin treatment for at least 3 months prior to screening
3. Subjects with haemoglobin between 10 g/dl to 12 g/dl
4. Subjects who are on clinically stable haemodialysis (defined as no clinically relevant changes of dialysis regimen and/or dialyzer) for at least 3 months prior to screening
5. Subject who had an adequacy of dialysis treatment measured by Kt/V
 - a. Kt/V must be ≥ 1.2 for subjects with 3 times of HD/week
 - b. Kt/V must be ≥ 1.8 for subjects with 2 times of HD/week
6. Subjects willing to provide a written informed consent
7. Subjects with serum ferritin $\geq 200 \mu\text{g/L}$ and/or transferrin saturation $\geq 20\%$
8. Subjects with a life expectancy more than at least study period in clinical judgment of the investigator

*CKD staging will be based on the five-stage system for classification of CKD based on KDIGO guidelines (page no: 32).

GFR will be calculated based on the EPI equation as below ([18](#))

$$\text{GFR} = 141 \times \min(S_{\text{cr}} / \kappa, 1)^{\alpha} \times \max(S_{\text{cr}} / \kappa, 1)^{-1.209} \times 0.993^{\text{Age}} \times 1.018 \text{ [if female]} \times 1.159 \text{ [if black]}$$

where:

S_{cr} is serum creatinine in mg/dL,
 κ is 0.7 for females and 0.9 for males,
 α is -0.329 for females and -0.411 for males,
min indicates the minimum of S_{cr} / κ or 1, and
max indicates the maximum of S_{cr} / κ or 1.

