4.1.2 Eligibility criteria at Baseline

Subjects must satisfy all of the following criteria to be included in the study:

1. Subjects with stable haemoglobin levels between 10 g/dl to 12.5 g/dl with stable EPREX dosage and intra-individual change in Hb of $\leq 1.2 \text{ g/dl}$ over 4 weeks before randomization
2. Subjects with serum ferritin $\geq 200 \mu\text{g/L}$ and/or transferrin saturation $\geq 20\%$

Patients who don't meet the eligibility criteria at baseline will be considered as screen failures.

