5.1.1 Method of Assigning Subjects to Treatments and Blinding

Subjects selected for participation will be randomly assigned to one of the two treatment arms, 264 subjects will be assigned to either treatment arm A (receiving EPIAO) or B (receiving EPREX) in a ratio of 1:1.

The randomization schedule will be generated by EA statistical team, using PROC PLAN in SAS, version 9.2 or higher, according to EA standard operating procedures (SOPs), listing subject randomization code number and treatment. The randomization allocation will be done by Interactive Voice Response System/ Interactive Web Response System (IVRS/IWRS) for dispensing the test drugs.

The investigator and sponsor's Medical and Safety Expert will have to contact the IVRS/IWRS for information regarding the identity of treatment sequence for each subject.

All subjects, who sign an IRB/IEC approved informed consent form and authorization for the use and disclosure of protected health information, will be assigned a unique subject identity code (SIC) consisting of two digit center code and three digit subject specific code. The randomization code will be captured separately as an additional identity.

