6.1 Screening / Visit 0 (Day -31 to Day 0)

Subjects considered likely to be eligible based on a pre-screening assessment will attend a screening assessment. Subjects will be screened to ensure enrolment of appropriate number of subjects into the study. The duration of screening period will be from Day -31 to Day 0. The Principal Investigator (PI) or his designee will explain the nature of the study, give full details and obtain a written informed consent from the subject prior to their participation in any study related procedures.

All inclusion/exclusion criteria will be assessed, demographic characteristics and vital signs will be recorded. A full physical examination will be performed. A detailed medical history will be elicited regarding symptoms, prior use of medications and prior medical/surgical therapies. Concomitant medications which are still on-going will be recorded at this visit. Laboratory investigations including haematology, serum chemistry and urinalysis (Appendix I) will be performed. Urinalysis test will be considered as optional for CKD patients as CKD patients may not be able to provide sufficient urine volume for urinalysis test due to low urine output. Serology and iron study will also be performed at screening visit. Menstrual and reproductive history will be recorded for all female subjects at this visit, including marital status, type of contraceptive used and details of menstrual cycle. Serum pregnancy test for women of childbearing potential will be done at the screening visit.

The Investigator will maintain a log of all the subjects screened for study participation and will record the reason(s) for excluding potential subjects. The subjects who successfully pass the screening tests and meet the inclusion exclusion criteria will be enrolled for the study.

Subjects 18 years of age or older must provide a signed, IRB approved written informed consent. No study related procedures or activities will be performed until each subject is fully informed and the consent form is signed and dated. All subjects will be given a copy of the signed and dated consent form.

The following assessments will be performed;

- Written informed consent
- Demographic data [i.e., date of birth, gender, race, weight (pre and post hemodialysis) and height]
- Detailed medical history with prior concomitant medication
- Menstrual and reproductive history (only for female subjects)
- Review and document inclusion and exclusion criteria

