If subject fails to achieve target range Hb and intra individual change of ≤ 1.2 g/dl at Extended Week 16/Extended Day 112 (EV9), such subject will continue the extension of titration period [Extended Week 18 (EV10/Extended Day 126) and Extended Week 20 (EV11/Extended Day 140)]. The extended titration period will be performed every two weeks. The assessment which will be performed in the extended titration period every two weeks will be similar to visit 7 assessments (Week 12/ Day 84). The target Hb range and intra individual change in Hb will be compared over Extended Week 16/Extended Day 112 (EV9), Extended Week 18/ Extended Day 126 (EV10) and Extended Week 20/ Extended Day 140 (EV11). If the subject with target range Hb and intra individual change of ≤ 1.2 g/dl is achieved during Extended Week 20/Extended Day 140 (EV11), subject will be scheduled in next week for randomization and will perform V8 procedure.

If the subject fails to achieve target range Hb and intra individual change of ≤ 1.2 g/dl at Extended Week 20/Extended Day 140 (EV11), such subject will be considered as screen failure.

The following assessments will be performed at week 2/Day 14, week 6/Day 42 and week 10/Day 70 at defined visit window;

- Demographic data (body weight: pre and post hemodialysis)

- Physical examination
- Vital signs
- Complete Blood Count (CBC)
- Adverse events
- Concomitant medication
- Dose adjustment if required as per section 5.1.7

The following assessments will be performed at the end of week 4/Day 28, week 8/ Day 56 and week 12/ Day 84;

- Demographic data (body weight: pre and post hemodialysis)
- Physical examination
- Vital signs
- Adverse events
- Concomitant medication
- Dose adjustment if required as per section 5.1.7
- Immunogenicity testing for anti-EPO antibody*
- Hematology
 - ✓ Haemoglobin
 - ✓ Haematocrit
 - ✓ Total WBC count
 - ✓ Differential WBC count
 - ✓ Platelet count
 - ✓ Red Blood Cell count
 - ✓ Reticulocyte count&
 - ✓ MCV
 - ✓ MCH
 - ✓ MCHC
 - ✓ Peripheral smear
 - ✓ Iron study#

* Only during week 8

Only during week 10

& Only during week 12/Day 84

The following assessments will be performed at the end of Extended Week 14/Extended Day 98 (EV8), Extended Week 16/ Extended Day 112 (EV9), Extended Week 18/Extended Day 126 (EV10) and Extended Week 20/Extended Day 140 (EV11) (as applicable for extended titration period) with window period of ± 2 days

- Demographic data (body weight: pre and post hemodialysis)
- Physical examination

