6.3 Randomization / Visit 8 (Day 91+3 / Week 13)

After the titration period of at least 3 months (or extended titration period of 2 months) with window period of ± 2 days, subjects who successfully fulfill the eligibility criteria at any of baseline visits will qualify for randomization and will be randomized to appropriate arm as per the study design. A negative serum pregnancy test is a must for females of child-bearing potential prior to randomization. If the subjects do not meet the eligibility criteria at the baseline visit, they will be considered as screen failures and will be discontinued from the study.

At this visit, vital signs will be recorded and physical examination will be done. AEs and concomitant medication will be recorded. The blood pressure will be monitored after the haemodialysis procedure and if the blood pressure is within the normal range then the study medication will be administrated by the study nurse or designee. If systolic pressure >160 mmHg, the blood pressure will be monitored after half an hour. If the BP does not decrease then the subject

will be asked to come the next day for drug administration. Assessments will be completed as per the study visit plan.

The following assessments will be performed;

- Demographic data (body weight: pre and post hemodialysis)
- Review and document eligibility criteria (Hb should be within the target range of 10 to 12.5 g/dl at visit 8 and intra individual change in Hb of ≤ 1.2 g/dl over previous 4 weeks i.e. over V5/V6/V7 or V7/EV8/EV9 or EV9/EV10/EV11).
- Serum pregnancy test
- Vital signs
- Adverse events
- Concomitant medication
- Physical examination
- Randomization of subjects
- CBC
- BUN (pre and post hemodialysis)
- Iron study
- Immunogenicity testing for anti-EPO antibody
- Adequacy of dialysis measurement by Kt/V formula

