9.8 Sample Size Determination

A sample size of 112 subjects per group is calculated to achieve a power of more than 80% for proof of equivalence for both co-primary endpoints. Considering 2 stratification factors i.e. body weight (Kg): ≤ 58 , $59-74$ & ≥ 75 , Hb level (g/dl): $10 - 11$ & $> 11 - 12$ and to balance between the two treatment groups in Thailand and Russia, the total number of subjects to be randomized is estimated to be 264 (n=132 subjects in each group) since a drop-out rate of approximately 18% was expected.

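### Do haemoglobin strata that stop at 12 g/dl leave eligible subjects up to 12.5 g/dl without a stratum?

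*Protocol*

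**What the plan says.** **Strata.** The synopsis (Planned Sample Size) names two stratification factors: body weight in three classes and haemoglobin in two, "Hb level (g/dl): 10 – 11 & > 11 – 12". Section 9.8 repeats them. Section 5.1.1 describes a generated schedule and central allocation by IVRS/IWRS, but names neither the factors nor the visit whose values feed them.

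**Range at screening.** Section 4.1.1 admits "Subjects with haemoglobin between 10 g/dl to 12 g/dl".

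**Range at randomisation.** Section 4.1.2 admits "Subjects with stable haemoglobin levels between 10 g/dl to 12.5 g/dl with stable EPREX dosage", and section 6.3 repeats the upper limit for the visit itself: "Hb should be within the target range of 10 to 12.5 g/dl at visit 8".

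**Analysis.** Section 9.4.1 fits an ANCOVA for each co-primary endpoint with centre, haemoglobin level and weight as covariates. It gives no time point for the haemoglobin covariate.

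**Related endpoint.** Section 3.1.3 lists the proportion of subjects with any haemoglobin value outside the target range in the double-blind period, without limits. The neighbouring endpoint states 10 to 12 g/dl. Section 9.4.2 plans descriptive summaries for both.

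**The concern.** Stratification classes should cover every subject who can be randomised, without overlap. Subjects are randomised at Visit 8, where values up to 12.5 g/dl are admitted, and the written classes end at 12. Read together, sections 4.1.2, 6.3 and 9.8 seem to leave a band of eligible subjects with nowhere to go.

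The alternative is that screening haemoglobin stratifies. The classes then fit, but the value is several months old at randomisation and predates the EPREX titration that sets the baseline.

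If sites or system builders resolved this differently, haemoglobin balance between the arms could be weaker than intended, and the stratification factor would be poorly documented.

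The endpoint without limits raises a similar worry. Two haemoglobin ranges occur in the protocol, 10 to 12.5 and 10 to 12 g/dl, and the reported proportion depends on which one is applied.

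**Working it through.** **1. Ranges side by side**

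| Source | Range (g/dl) |
|---|---|
| Strata (synopsis, 9.8) | 10–11 and >11–12, together 10–12 |
| Screening (4.1.1) | 10–12 |
| Baseline (4.1.2) and Visit 8 (6.3) | 10–12.5 |

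The strata cover the whole screening range. Of the Visit 8 range they cover (12 − 10)/(12.5 − 10) = 2.0/2.5 = 80% of the width. The gap therefore exists only if the Visit 8 value stratifies, and no section says that it does.

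**2. Age of a screening value at randomisation**

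Section 6.1 states: "The duration of screening period will be from Day -31 to Day 0". Standard randomisation is at Day 91. On the longest titration route (section 6.2) it falls one week after Day 140, so at about Day 147.

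- Shortest: Day 0 to Day 91 = 91 days; 91/7 = 13.0 weeks.
- Longest: Day −31 to Day 147 = 178 days; 178/7 = 25.4 weeks.

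An older value predicts later haemoglobin less well, so it is a less efficient stratifier. It is still a pre-randomisation value and therefore a valid one.

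**3. How many subjects could fall in the gap if Visit 8 stratifies**

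The protocol gives no baseline haemoglobin distribution, so the means and SDs below are assumptions. With values recorded to 0.1 g/dl and a normal distribution limited to 10.0–12.5,

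share = [Φ(12.55) − Φ(12.05)] / [Φ(12.55) − Φ(9.95)],

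where Φ(x) is the normal distribution function with the stated mean and SD. For mean 11.0 and SD 0.6 this is (0.9951 − 0.9599)/(0.9951 − 0.0401) = 0.0352/0.9550 = 3.7%.

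| Mean / SD | Share at 12.1–12.5 | Of 264 |
|---|---|---|
| 11.0 / 0.6 | 3.7% | 9.7 |
| 11.0 / 0.7 | 5.8% | 15.3 |
| 11.2 / 0.7 | 9.1% | 24.1 |
| 11.5 / 0.6 | 14.6% | 38.6 |
| 11.5 / 0.7 | 16.2% | 42.8 |

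So about 10 to 43 subjects would need a class. This says nothing about imbalance. If the upper class is simply run as everything above 11, all of them enter it and the layout stays at 2 haemoglobin × 3 weight = 6 cells.

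**4. What could reach the primary result**

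- Any candidate value (screening, Visit 7 or Visit 8) precedes allocation, so the choice among them cannot bias the treatment comparison.
- Haemoglobin level is in the ANCOVA, so a chance imbalance on it is adjusted for.
- The 112 per group, 132 per group and 264 in total do not depend on where the strata end.

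**5. The endpoint without limits**

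This trial attaches a figure to the label 'target range' in the synopsis (Study Design) and in sections 3.1.2, 5.1.7 (titration), 6.2 and 6.3. Each time it is 10 to 12.5 g/dl. Section 5.1.7 then reuses the label for the treatment period without a figure. The 10 to 12 g/dl treatment-period goal in section 5.1.7 and the neighbouring endpoint in 3.1.3 do not use the label.

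Because 10–12 lies inside 10–12.5, the proportion outside the narrower range can only be equal or larger, in both arms. The size of the difference cannot be worked out from the protocol: the endpoint counts a subject with any value out of range across many visits, and that depends on a within-subject correlation that is not given.

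**The case for a change.** The best case for acting is that this is not pure omission. The protocol itself writes numeric strata and a numeric eligibility range for the randomisation visit, and they do not match. Nothing directs the reader to a screening value that is 13 to 25 weeks old. The correction would be a few words and no patients. For the endpoint, both ranges can be defended from the text, and a figure fixed before the unblinded interim analysis of section 9.6 would rule out a later choice.

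The observations stand: the ranges differ, the visit is not named and the endpoint carries no limits of its own. The conclusion that the design is faulty does not follow. A mismatch needs the premise that Visit 8 haemoglobin stratifies, and the text does not supply it. The classes appear only in a sample-size sentence, which is not a randomisation specification. Its weight classes are shorthand too: 58.5 kg fits none of ≤58, 59–74 and ≥75 unless weights are rounded. A central system cannot allocate a subject without a class, so whoever built it had to settle both the visit and the upper limit.

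The endpoint's limits are ordinary content of a statistical analysis plan, which would be settled before unblinding. The protocol's own numeric use of the label points to one reading, the endpoint carries no test or margin, and both proportions could be reported.

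**Conclusion.** No change is needed. The strata match the screening range and are complete on that reading. On the other reading, running the upper class as above 11 g/dl closes the gap without altering the number of cells. What remains is an unnamed visit, which belongs in the randomisation specification, and an endpoint range, which belongs in the statistical analysis plan.

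The stakes are limited to allocation balance on a factor already in the ANCOVA, and to one descriptive proportion. The primary comparison is not biased, and sample size, power and alpha do not move. The count of about 10 to 43 of 264 subjects rests on assumed means of 11.0 to 11.5 and SDs of 0.6 to 0.7 g/dl, and measures classification only.

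The conclusion assumes that one haemoglobin value and one rule for the upper class were applied throughout by the central system; the protocol neither shows nor contradicts this. Which haemoglobin goal is clinically appropriate in each phase is not judged here.

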SOPs	Standard Operating Procedures
SUSAR	Suspected Unexpected Serious Adverse Reaction
TIBC	Total Iron Binding Capacity
TSAT	Serum transferrin saturation
WBC	White Blood Cell
WHO – DDE	World Health Organization Drug Dictionary Enhanced
Wt	Weight

1 INTRODUCTION AND BACKGROUND INFORMATION

Chronic kidney disease (CKD) is a general term for heterogeneous disorders affecting the structure and function of the kidney. The variation in disease expression is related partly to cause and pathology, severity, and rate of progression. The definition of CKD is based on the presence of kidney damage (ie, albuminuria) or decreased kidney function (ie, glomerular filtration rate [GFR] <60 mL/min per 1·73 m²) for 3 months or more, irrespective of clinical diagnosis (1).

Clinical guidelines define a five-stage system for classification of CKD (Kidney Disease Improving Global Outcome [KDIGO] Guidelines).

CKD STAGE	DESCRIPTION	GFR (ml/min per 1.73 m ²)
1	Kidney damage with normal or increased GFR	≥90
2	Kidney damage with mild decreased GFR	60-89
3	Moderate decreased GFR	30-59
4	Severe decreased GFR	15-29
5	Kidney failure	< 15 (or dialysis)

Secondary to the functional abnormality due to CKD, there is a decreased production of the erythropoietin, a glycoprotein hormone produced primarily by the kidney in response to hypoxia and which is the key regulator of red blood cell (RBC) production. Erythropoietin is involved in all phases of erythroid development, and has its principal effect at the level of erythroid precursors. Thus anaemia is a common complication of CKD. Although anaemia in subjects with CKD may develop in response to a wide variety of causes, the primary cause of anaemia associated with CKD is deficiency of erythropoietin. Other factors in the genesis of renal anaemia include functional or absolute iron deficiency, blood loss and presence of uraemic inhibitors (for example, parathyroid hormone, inflammatory cytokines) and deficiencies of folate or Vitamin B12 (2).

The primary therapeutic options for the anaemia of CKD include iron supplementation, erythropoiesis-stimulating agents (ESAs) and RBC transfusions. In subjects with CKD but stable kidney function, the appearance or progression of anaemia may herald a new problem that is causing blood loss or is interfering with red cell production. Thus anaemia should be evaluated independently of CKD stage in order to identify any reversible process contributing to the anaemia. (3) Early treatment of anaemia may reduce cardiovascular morbidity and improve quality of life.

The introduction of recombinant human erythropoietin (r-HuEPO) into clinical practice in the 1980 s was a major breakthrough in the treatment of the anaemia of subjects with CKD. The development of r-HuEPO was aimed at replacing the insufficient endogenous erythropoietin (EPO) production related to CKD progression. r-HuEPO administration was regarded by the nephrology community as a beneficial therapy for long-term dialysis subjects whose haemoglobin values fell to extremely low levels, making them transfusion-dependent (3). r-HuEPO stimulates erythropoiesis in anaemic subjects with chronic renal failure in whom the endogenous production of erythropoietin is impaired. Because of the length of time required for erythropoiesis – several

days for erythroid progenitors to mature and be released into the circulation – a clinically significant increase in haemoglobin is usually not observed in less than two weeks and may require up to ten weeks in some subjects. (4).

Erythropoietin interacts directly with the EPO receptor on the RBC surface, triggering activation of several signal transduction pathways, resulting in the proliferation and terminal differentiation of erythroid precursor cells and providing protection from RBC precursor apoptosis. The magnitude of increase in RBC concentration in response to administration of r-HuEPO is primarily controlled by the length of time EPO concentrations are maintained, not by the EPO concentration level. Subcutaneous (SC) EPO administration results in slower absorption than IV administration, leading to lower peak plasma levels and an apparent extended terminal half-life. However, SC administration is associated with an increased risk of immunogenicity compared with IV administration (5).

EPIAO was approved for marketing in China in 1998. Currently, it is also approved for marketing in another 16 countries including Pakistan, Sri Lanka, Brazil, Egypt, Dominica, Trinidad & Tobago, Thailand, Philippines, Columbia, Mongolia, Guatemala, Salvador, Palestine, Azerbaijan, Myanmar, and Cambodia. So far, China and Thailand are the biggest EPIAO markets in worldwide. Since the marketing approval, it is estimated that about 587,897 domestic and foreign subjects have used EPIAO for the treatment of anaemia. (6)

